8.2.4. Adverse Event Summaries

An overall summary of AEs by cohort will include:

- Number (%) of subjects reporting any TEAEs
- Number (%) of subjects reporting any SAEs
- Number (%) of subjects reporting any Grade 3 or higher TEAEs
- Number (%) of subjects reporting any TEAEs related to INCB054828
- Number (%) of subjects who temporarily interrupted INCB054828 because of TEAEs
- Number (%) of subjects who permanently discontinued INCB054828 because of TEAEs
- Number (%) of subjects with INCB054828 dose reductions because of TEAEs
- Number (%) of subjects who had a fatal TEAE

The following summaries for each cohort will be produced by MedDRA term (if ≤ 10 subjects appear in a table, a listing may be appropriate):

- Summary of TEAEs by system organ class and preferred term
- Summary of TEAEs by preferred term in decreasing order of frequency
- Summary of TEAEs by system organ class, preferred term, and maximum severity
- Summary of Grade 3 or higher TEAEs by system organ class and preferred term
- Summary of Grade 3 or higher TEAEs by preferred term in decreasing order of frequency
- Summary of treatment-related TEAEs by system organ class and preferred term
- Summary of treatment-related TEAEs by preferred term in decreasing order of frequency
- Summary of Grade 3 or higher treatment-related AEs by system organ class and preferred term
- Summary of TEAEs with a fatal outcome by system organ class and preferred term
- Summary of serious TEAEs by system organ class and preferred term
- Summary of treatment-emergent SAEs by preferred term in decreasing order of frequency
- Summary of treatment-related serious TEAEs by system organ class and preferred term
- Summary of TEAEs leading to dose reduction by system organ class and preferred term
- Summary of TEAEs leading to dose interruption by system organ class and preferred term
- Summary of TEAEs leading to discontinuation of study drug by system organ class and preferred term
- Summary of treatment-emergent non-SAEs by system organ class and preferred term
- Summary of TEAEs and Grade 3 or higher AEs by preferred term in decreasing order of frequency
- Summary of clinically notable TEAEs by category and preferred term

- Summary of Grade 3 or higher clinically notable TEAEs by category and preferred term
- Summary of serious clinically notable TEAEs by category and preferred term
- Summary of clinically notable TEAEs leading to dose reduction by category and preferred term
- Summary of clinically notable TEAEs leading to dose interruption by category and preferred term
- Summary of clinically notable TEAEs leading to discontinuation of study drug by category and preferred term
- Summary of clinically notable TEAEs by category and preferred term: life-table method
- Summary of Grade 3 or higher clinically notable TEAEs by category and preferred term: life-table method

8.3. Clinical Laboratory Tests

8.3.1. Laboratory Value Definitions

For numeric laboratory results, the change and percentage change from baseline will be calculated. Baseline will be determined according to Section 4.1.3. If there are multiple values that meet the criteria for baseline, the value from the central laboratory has priority over the value from the local laboratory. Thereafter, additional rules may be provided after consultation with the medical monitor to delineate which value will be defined as baseline.

Laboratory test values outside of the normal range will be assessed for severity based on CTCAE grade or similar criteria where clinical intervention is required for CTCAE grading.

8.3.2. Laboratory Value Summaries

All test results and associated normal ranges from central laboratories will be reported in SI units. All tests with numeric values will have a unique unit per test. Any laboratory test results and associated normal ranges from local laboratories will be converted to SI units.

For numeric laboratory values, baseline value, postbaseline value, change from baseline, and percent change from baseline will be summarized by visit. In addition, mean change from baseline will be plotted over time for selected laboratory parameters, including phosphate, calcium, sodium, 1,25-dihydroxyvitamin D, 25-hydroxyvitamin D, and parathyroid hormone.

For the laboratory parameters that have CTCAE grading, shift tables will also be presented showing change in CTCAE severity grade from baseline to worst grade postbaseline. The

denominator for the percentage calculation will be the number of subjects in the baseline category.

Categorical laboratory data will be tabulated by visit at baseline and postbaseline visits where appropriate.

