Note that a grading scale for hyperphosphatemia (elevated serum phosphate) is not included in CTCAE v 4.03. Grading should be applied using the table above ("investigations-other, specify" category in CTCAE v 4.03). Hyperphosphatemia should be graded based on clinical severity (eg, symptoms) and medical intervention measures taken (eg, phosphate binders) and not on phosphate levels.

The occurrence of AEs should be sought by nondirective questioning of the subject during the screening process after signing the ICF and at each visit during the study. Adverse events may also be detected when they are volunteered by the subject during the screening process or between visits, or through physical examination, laboratory test, or other assessments. To the extent possible, each AE should be evaluated to determine:

- The severity grade (CTCAE Grade 1 to 4).
- Whether there is at least a reasonable possibility that the AE is related to the study treatment: suspected (yes) or not suspected (no).
- The start and end dates, unless unresolved at final follow-up.
- The action taken with regard to study drug.
- The event outcome (eg, not recovered/not resolved, recovered/resolved, recovering/resolving, recovered/resolved with sequelae, fatal, unknown).
- The seriousness, as per serious adverse event (SAE) definition provided in Section 8.3.1.

Unlike routine safety assessments, SAEs are monitored continuously and have special reporting requirements (see Section 8.3.2).

All AEs should be treated appropriately. If an AE is treated with a concomitant medication or nondrug therapy, this action should be recorded on Adverse Event form and the treatment should be specified on the Prior/Concomitant Medications or Procedures and Non-Drug Therapy form in the eCRF.

Once an AE is detected, it should be followed until it has resolved or until it is judged to be permanent; assessment should be made at each visit (or more frequently if necessary) of any changes in severity, the suspected relationship to the study drug, the interventions required to treat the event, and the outcome.

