9.4.2.2. Clinical Laboratory Tests

Laboratory test values outside the normal range will be assessed for severity based on the normal ranges for the clinical reference laboratory. The incidence of abnormal laboratory values and shift tables relative to baseline will be tabulated.

Laboratory data will be classified into Grades 1 through 4 using CTCAE v4.03. The following summaries will be produced for the laboratory data:

- Number and percentage of subjects with worst postbaseline CTCAE grade (regardless of baseline value). Each subject will be counted only for the worst grade observed postbaseline.
- Shift tables from baseline to the worst postbaseline value using CTCAE grade.
- For laboratory parameters where CTCAE grades are not defined, shift tables to the worst postbaseline value using the low/normal/high classifications based on laboratory reference ranges.

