3.2.14	Summary of Treatment-Emergent Adverse Events Leading to INCB054828 Dose Reduction by MedDRA System Organ Class and Preferred Term	Safety
3.2.15	Summary of Treatment-Emergent Adverse Events Leading to INCB054828 Dose Interruption by MedDRA System Organ Class and Preferred Term	Safety
3.2.16	Summary of Treatment-Emergent Adverse Events Leading to Discontinuation of INCB054828 by MedDRA System Organ Class and Preferred Term	Safety
3.2.17	Summary of Treatment-Emergent Non-Serious Adverse Events by MedDRA System Organ Class and Preferred Term	Safety
3.2.18	Summary of Treatment-Emergent Adverse Events and Grade 3 or Higher Adverse Events by MedDRA Preferred Term in Decreasing Order of Frequency	Safety
3.2.19	Summary of Sponsor-Defined Clinically Notable Treatment-Emergent Adverse Events by Category and Preferred Term	Safety
3.2.20	Summary of Grade 3 or Higher Sponsor-Defined Clinically Notable Treatment-Emergent Adverse Events by Category and Preferred Term	Safety
3.2.21	Summary of Serious Sponsor-Defined Clinically Notable Treatment-Emergent Adverse Events by Category and Preferred Term	Safety

Table No.	Title	Population
3.2.22	Summary of Sponsor-Defined Clinically Notable Treatment-Emergent Adverse Events Leading to Dose Reduction by Category and Preferred Term	Safety
3.2.23	Summary of Sponsor-Defined Clinically Notable Treatment-Emergent Adverse Events Leading to Dose Interruption by Category and Preferred Term	Safety
3.2.24	Summary of Sponsor-Defined Clinically Notable Treatment-Emergent Adverse Events Leading to Discontinuation of Study Drug by Category and Preferred Term	Safety
3.2.25	Summary of Sponsor-Defined Clinically Notable Treatment-Emergent Adverse Events by Category and Preferred Term: Life-Table Method	Safety
3.2.26	Summary of Grade 3 or Higher Sponsor-Defined Clinically Notable Treatment-Emergent Adverse Events by Category and Preferred Term: Life-Table Method	Safety
Laboratory		
3.3.1	Summary of Laboratory Values – Hematology	Safety
3.3.2	Shift Summary of Hematology Values in CTC Grade – To the Worst Abnormal Value	Safety
3.3.3	Summary of Treatment-Emergent Worsening of Laboratory Abnormalities – Hematology	Safety
3.3.4	Summary of Laboratory Values – Chemistry	Safety
3.3.5	Shift Summary of Chemistry Values in CTC Grade – To the Worst Abnormal Value	Safety
3.3.6	Summary of Treatment-Emergent Worsening of Laboratory Abnormalities – Chemistry	Safety
3.3.7	Summary of Laboratory Values – Coagulation	Safety

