3.3.8	Shift Summary of Coagulation Values in CTC Grade – To the Worst Abnormal Value	Safety
3.3.9	Summary of Treatment-Emergent Worsening of Laboratory Abnormalities – Coagulation	Safety
3.3.10	Summary of Laboratory Values – Urinalysis	Safety
Vital Signs		
3.4.1	Summary of Systolic Blood Pressure	Safety
3.4.2	Summary of Diastolic Blood Pressure	Safety
3.4.3	Summary of Pulse	Safety
3.4.4	Summary of Body Temperature	Safety
3.4.5	Summary of Respiratory Rate	Safety
3.4.6	Summary of Body Weight	Safety
ECG		
3.5.1	Summary of PR Interval (ms) From 12-Lead ECG	Safety
3.5.2	Summary of QRS Interval (ms) From 12-Lead ECG	Safety
3.5.3	Summary of QT Interval (ms) From 12-Lead ECG	Safety
3.5.4	Summary of QTcF Interval (ms) From 12-Lead ECG	Safety
3.5.5	Summary of Heart Rate (bpm) From 12-Lead ECG	Safety
3.5.6	Summary of Outliers of QT and QTcF Interval Values From 12-Lead ECG	Safety
3.5.7	Summary of Clinically Significant ECG Abnormalities	Safety

Figures

Figure No.	Title
4.1	Forest Plot of Objective Response Rate (Efficacy)
4.2.1	Kaplan-Meier Estimates of Progression-Free Survival (Efficacy)
4.2.2	Kaplan-Meier Estimates of Duration of Response (Efficacy)
4.2.3	Kaplan-Meier Estimates of Overall Survival (Efficacy)
4.3.1	Waterfall Plot of Best Percent Change of Target Lesion Size From Baseline (Efficacy)
4.3.2	Swimmer Plot of Duration of Treatment (Efficacy)
4.3.3	Forest Plot of Progression-Free Survival (Efficacy)
4.3.4	Forest Plot of Duration of Response (Efficacy)
4.5	Kaplan-Meier Estimates of Time to Adverse Event (Safety)
4.6	Line Graph of Mean Change From Baseline for Selected Laboratory Values (Safety)

Listings

Listing No.	Title
2.1.1	Analysis Population
2.1.2	Subject Enrollment and Disposition Status
2.1.3	Subject Inclusion and Exclusion Criteria Violations
2.2.1	Protocol Deviations
2.4.1	Demographic and Baseline Characteristics
2.4.2	Oncology Disease History
2.4.3	Prior Systemic Therapy
2.4.4	Prior Surgery or Surgical Procedure
2.4.5	Prior Radiation Treatment
2.4.6	Post Therapy
2.4.7	Medical History
2.4.8	Hepatitis History
2.4.9	Prior and Concomitant Medication
2.4.10	FGF/FGFR Alterations
2.5	Study Drug Compliance
2.6.1	Best Overall Response, Duration of Response, Progression-Free Survival, and Overall Survival
2.6.2	Investigator-Reported Assessment by RECIST v1.1
2.6.3	Response Assessment: Target Lesions
2.6.4	Response Assessment: Non-target Lesions
2.6.5	Response Assessment: New Lesions

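### The SAP drops the protocol's low/normal/high laboratory shift tables and raises the notable QTcF cut-off from > 450 to > 460 ms, while SAP 10.1 declares no change

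*SAP*

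**What the plan says.** **Laboratory.** Protocol 9.4.2.2 makes two shift-table commitments. One is by CTCAE grade. The other begins "For laboratory parameters where CTCAE grades are not defined, shift tables to the worst postbaseline value using the low/normal/high classifications" and takes the categories from laboratory reference ranges. SAP 8.3.2 carries over only the first: "For the laboratory parameters that have CTCAE grading, shift tables will also be presented showing change in CTCAE severity grade". Its other categorical output is a tabulation by visit.

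SAP 8.3.1 adds that "Laboratory test values outside of the normal range will be assessed for severity based on CTCAE grade or similar criteria", the second option being for parameters whose CTCAE grading depends on intervention. It does not say what those criteria are.

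The shift tables in SAP Appendix A are 3.3.2 ("Shift Summary of Hematology Values in CTC Grade"), 3.3.5 ("Shift Summary of Chemistry Values in CTC Grade") and 3.3.8 ("Shift Summary of Coagulation Values in CTC Grade"). Tables 3.3.3, 3.3.6 and 3.3.9 share the title "Summary of Treatment-Emergent Worsening of Laboratory Abnormalities", one per panel, and their content is not described.

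On phosphate, Protocol 8.1.2 states that "a grading scale for hyperphosphatemia (elevated serum phosphate) is not included in CTCAE v 4.03". It directs that the adverse event be graded on symptoms and treatment given, not on the measured level.

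**ECG.** Protocol 9.4.2.4 (Table 10) sets the notable QTcF limit at > 450 msec. SAP 8.5 (Table 6) sets it at > 460 ms. In both documents the limit decides what goes into a listing.

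**Declared changes.** SAP 10.1, the place to record departures from the protocol's analyses, reports none, and SAP 10.2 mentions neither point. SAP 2.1 bases the SAP on Amendment 6 and says it stays in force for later amendments.

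**The concern.** The two departures are unrelated, but both are undeclared.

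The laboratory one matters because Protocol 5.4.3 describes raised phosphate as the expected on-target effect of the drug. The by-visit statistics in SAP 5.1 and 8.3.2 (mean, standard deviation, median, minimum, maximum) do not show how many subjects ever reached a high value, because each visit is summarised separately. Adverse event tables do not fill the gap either. Under Protocol 8.1.1 an abnormal laboratory value becomes an adverse event only if it causes signs or symptoms, is judged clinically meaningful, needs therapy, or changes study drug.

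The ECG one matters because the same QTcF value is notable under one document and not under the other. Protocol exclusion criterion 9 bars a screening QTcF above 450 ms. An on-study value between the two limits is therefore above the trial's own entry limit, yet it would not appear in the SAP's notable listing.

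**Working it through.** There is no power, alpha or effect size to recompute. The check is a side-by-side reading with simple counts.

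**Step 1. Laboratory tables in SAP Appendix A**

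| Type | Table numbers | Count |
|---|---|---|
| Value summaries | 3.3.1, 3.3.4, 3.3.7, 3.3.10 | 4 |
| Shift in CTC grade | 3.3.2, 3.3.5, 3.3.8 | 3 |
| Treatment-emergent worsening, content undefined | 3.3.3, 3.3.6, 3.3.9 | 3 |
| Low/normal/high shift | none | 0 |

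4 + 3 + 3 + 0 = 10. The numbering is unbroken and the vital-sign tables follow directly, so no laboratory table is missing from the run.

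**Step 2. What happens to high phosphate**

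- If phosphate is treated as a parameter without CTCAE grades, the protocol promises it a low/normal/high shift table, and the SAP has none.
- If it is treated as graded, it enters Table 3.3.5. By Protocol 8.1.2 there is no v4.03 grade for the high direction, so a CTC-grade shift cannot show a rise.

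Either way, no SAP table is defined so that it must count subjects by worst high phosphate. Table 3.3.6 might do so, but its content is not stated. The alternative severity criteria in SAP 8.3.1 are not stated either, and they set a severity rule, not a table.

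**Step 3. Notable limits in the two documents**

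| Comparison | Limits | Equal | Different |
|---|---|---|---|
| Vital signs: Protocol Table 9 against SAP Table 5 | 5 parameters × 2 = 10 | 10 | 0 |
| ECG: Protocol Table 10 against SAP Table 6 | 4 parameters × 2 = 8 | 7 | 1 (QTcF high) |
| Total | 18 | 17 | 1 |

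The gap is 460 − 450 = 10 ms. A QTcF above 450 and up to 460 ms is notable under the protocol and not under the SAP. Such values stay in the by-visit QTcF summary (Table 3.5.4). Tables 3.5.6 (QT and QTcF outliers) and 3.5.7 (clinically significant ECG findings) may count some of them, but neither gives a cut-off, so they do not settle the conflict.

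**Step 4. Could a version difference explain it?** The SAP was written on Amendment 6 and the protocol supplied is Amendment 7. The Amendment 7 summary lists no change to Section 9.4.2 or Table 10, although it mentions unspecified administrative changes. Because the SAP says it holds for later amendments, the two current documents conflict in either case.

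**The case against.** The strongest objection is that the lost phosphate table would say little. Exclusion criterion 6d keeps out subjects above the institutional upper limit, and Protocol 1.1.1 reports that 100% of subjects at 13.5 mg in the Phase 1 study developed hyperphosphatemia. A three-category shift might show almost everyone moving to high, and not how high. That is fair, and it is why a tabulation by level is offered below as an option. It does not remove the commitment, which covers every parameter without CTCAE grades.

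Phosphate is also reported in other ways: an adverse event grouping with time-to-first-event analyses (SAP 8.2.2 and 8.2.3), Tables 3.2.19 to 3.2.26, the count of subjects with at least one event in Protocol 9.4.2.1, and a mean-change plot. This stands. The loss is the categorical shift, not all phosphate reporting.

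It can be said that the SAP is silent and does not expressly drop the tables. That is true of the wording. However, Appendix A is the list of planned outputs, and a table found in neither the text nor that list is not planned.

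The end of the SAP's listing catalogue is not in the public copy, so full laboratory or ECG value listings may exist. They would not be a shift table and would not settle which QTcF limit defines the notable listing. The amendment difference also means that it cannot be fully verified whether SAP 10.1 was inaccurate on the day it was written.

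Finally, a QTcF of 455 ms is not notable under the SAP's own table, so listing from > 450 ms follows the protocol's limit. It does not leave the choice open. That is correct. The argument for it is only that the wider listing contains everything the narrower one would show. The QTcF discontinuation criteria in Protocol 5.4.4 are untouched by any of this.

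**Conclusion.** The point holds on both parts. None of the ten planned laboratory tables is a low/normal/high shift, although the protocol promises such tables. One of the eight ECG limits (1 of 18 with vital signs) differs, by 10 ms. SAP 10.1 declares neither.

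This is a minor reconciliation that should still be made. It concerns descriptive safety output, and no primary or secondary efficacy result depends on it. The number of subjects affected cannot be derived from the documents, and none is claimed. The conclusion assumes that Appendix A is the full catalogue of planned laboratory tables, which its unbroken numbering supports, and that the undefined worsening tables are not meant to be the promised shifts. If the sponsor's table shells show otherwise for Table 3.3.6, the laboratory part reduces to a missing definition.

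**What to change.** 1. Add low/normal/high shift tables to the worst postbaseline value to SAP 8.3.2 and Appendix A for parameters without CTCAE grades. State explicitly that high phosphate is included even if phosphate is treated as graded in the other direction.
2. Define the content of Tables 3.3.3, 3.3.6 and 3.3.9 and the alternative severity criteria in SAP 8.3.1.
3. Optionally, and beyond what the protocol promises, tabulate worst postbaseline phosphate by the level bands already in Protocol Table 4 (> 5.5 to 7, > 7 to 10, and > 10 mg/dL). This would show the extent of the rise, which three categories cannot.
4. Reconcile the QTcF listing limit between Protocol Table 10 and SAP Table 6. Listing from > 450 ms, with values above 460 ms flagged, would show what either document calls for. This is a reporting limit only. State the cut-offs used in Table 3.5.6.
5. Record in SAP 10.1, with the reason, any departure that is kept.

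The cost is a few descriptive tables and one changed listing limit, all from data already collected, with no new assessments.

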8.4. Vital Signs

Values at each scheduled visit, change, and percent change from baseline for vital signs, including systolic blood pressure, diastolic blood pressure, pulse, respiratory rate, weight, and body temperature, will be summarized descriptively.

Criteria for clinically notable vital sign abnormalities are defined in [Table 5](#). The abnormal values for subjects exhibiting clinically notable vital sign abnormalities will be listed. Alert vital signs are defined as an absolute value outside of the defined range and percentage change from baseline greater than 25%. The abnormal values for subjects exhibiting alert vital sign abnormalities will also be listed.

Table 5: Criteria for Clinically Notable Vital Sign Abnormalities

Parameter	High Threshold	Low Threshold
Systolic blood pressure	> 155 mmHg	< 85 mmHg
Diastolic blood pressure	> 100 mmHg	< 40 mmHg
Pulse	> 100 bpm	< 45 bpm
Temperature	> 38°C	< 35.5°C
Respiratory rate	> 24 breaths/min	< 8 breaths/min

8.5. Electrocardiograms

Twelve-lead ECGs including PR, QRS, QT, and QTcF intervals, as well as heart rate, will be obtained for each subject during the study. Values at each scheduled visit, change, and percent change from baseline will be summarized for each ECG parameter. Change and percent change from baseline will be calculated using the average of all nonmissing values before the first dose of INCB054828 as the baseline value.

Criteria for clinically notable ECG abnormalities are defined in [Table 6](#). The abnormal values for subjects exhibiting clinically notable ECG abnormalities will be listed with study visit. Alert ECG values are defined as both the absolute value outside the defined range and the percentage change greater than 25% (QRS 30%). The abnormal values for subjects exhibiting alert ECG abnormalities will be identified and listed.

Table 6: Criteria for Clinically Notable Electrocardiogram Abnormalities

Parameter	High Threshold	Low Threshold
QTcF	> 460 ms	< 295 ms
PR	> 220 ms	< 75 ms
QRS	> 120 ms	< 50 ms
QT	> 500 ms	< 300 ms

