3.2. Subject Exclusion Criteria

A subject who meets any of the following criteria will be excluded from the study:

1. Prior receipt of selective FGFR inhibitor.
2. Treatment with other investigational study drug for any indication for any reason, or receipt of anticancer medications within 28 days before first dose of study drug. Subjects must have recovered (Grade ≤ 1 or at pretreatment baseline) from AEs from previously administered therapies.
3. Untreated brain or central nervous system (CNS) metastases or brain/CNS metastases that have progressed (eg, evidence of new or enlarging brain metastasis or new neurological symptoms attributable to brain/CNS metastases). Subjects with previously treated and clinically stable brain/CNS metastases and who are off all corticosteroids for ≥ 4 weeks are eligible.
4. Have a known additional malignancy that is progressing or requires active treatment. Exceptions include basal cell carcinoma of the skin, squamous cell carcinoma of the skin, carcinoma *in situ* of the cervix, or other noninvasive or indolent malignancy that has undergone potentially curative therapy.
5. Are pregnant or lactating.
6. Have abnormal laboratory parameters:
 - a. Total bilirubin $\geq 1.5 \times$ upper limit of normal (ULN; $\geq 2.5 \times$ ULN if Gilbert syndrome or disease involving liver).
 - b. AST and ALT $> 2.5 \times$ ULN (AST and ALT $> 5 \times$ ULN in the presence of liver metastases).
 - c. Creatinine clearance ≤ 30 mL/min based on Cockcroft-Gault.
 - d. Serum phosphate $>$ institutional ULN.
 - e. Serum calcium outside of the institutional normal range or serum albumin-correct calcium outside of the institutional normal range when serum albumin is outside of the institutional normal range.
 - f. Potassium levels $<$ institutional lower limit of normal; supplementation can be used to correct potassium level during the screening.
7. Known history of human immunodeficiency virus (HIV) infection or positivity on immunoassay confirmed per local standards (NOTE: HIV screening test is optional for US subjects, but subjects with known history of HIV infection will be excluded).
8. Evidence of active hepatitis B virus (HBV) or hepatitis C virus (HCV) infection.
9. Has a history or presence of an abnormal ECG that in the investigator's opinion is clinically meaningful. Subjects with a screening QTcF interval > 450 milliseconds are excluded.

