5.4.4. Criteria for Permanent Discontinuation of Study Drug

The occurrence of unacceptable toxicity not caused by the underlying malignancy will be presumed to be related to study drug treatment and will require that the study drug be permanently discontinued. Unacceptable toxicity is defined as follows:

- Occurrence of an AE that is related to treatment with the study drug that, in the judgment of the investigator or the sponsor's medical monitor, compromises the subject's ability to continue study-specific procedures or is considered to not be in the subject's best interest.
- An AE requiring more than 2 dose reductions.
- Persistent AE requiring a delay of therapy for more than 21 days unless a greater delay has been approved by the sponsor.
- Increase in QT/QTcF to > 500 milliseconds or to > 60 milliseconds over baseline. In case of a QTc > 500 milliseconds, the subject must be hospitalized and a continuous ECG monitoring must be set up until the measure of the QTc interval decreases below 500 milliseconds and until acceptable in the opinion of a local cardiologist.

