7.5.4. Electrocardiograms

All 12-lead ECGs will be performed with the subject in a recumbent or semirecumbent position after 5 minutes of rest.

The 12-lead ECGs will be interpreted by the investigator at the site to be used for immediate subject management. The decision to include or exclude a subject or withdraw a subject from the study based on an ECG flagged as "Abnormal, Clinically Significant" is the responsibility of the investigator, in consultation with the sponsor's medical monitor, as appropriate. Clinically notable abnormalities that are considered clinically significant in the judgment of the investigator are to be reported as AEs.

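### The SAP's ECG alert needs a QTcF rise of more than 92 ms, and no SAP text reports the Protocol's own limits of > 500 ms or > 60 ms over baseline

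*SAP*

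**What the plan says.** SAP 8.5 (Electrocardiograms) sets up two listings.

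- **Clinically notable values.** Any value outside the Table 6 range, which for QTcF means above 460 ms or below 295 ms, with no condition on change: "The abnormal values for subjects exhibiting clinically notable ECG abnormalities will be listed with study visit".
- **Alert values.** A narrower set that needs two conditions at once: "Alert ECG values are defined as both the absolute value outside the defined range and the percentage change greater than 25% (QRS 30"%). Change is calculated "using the average of all nonmissing values before the first dose of INCB054828 as the baseline value".

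SAP Appendix A also plans Table 3.5.6, "Summary of Outliers of QT and QTcF Interval Values From 12-Lead ECG". Only the title is given.

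Protocol 9.4.2.4 has the clinically notable ECG listing but no ECG alert. A 25% alert rule appears in the Protocol only for vital signs (9.4.2.3).

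Protocol 5.4.4 includes this in its definition of unacceptable toxicity: "Increase in QT/QTcF to > 500 milliseconds or to > 60 milliseconds over baseline". On entry, Protocol 3.2 item 9 says: "Subjects with a screening QTcF interval > 450 milliseconds are excluded".

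**The concern.** A 25% change can be a workable screen for pulse or blood pressure. QTcF varies over a much narrower relative range, and 25% of a 400 ms baseline is already 100 ms. An alert built on that percentage can stay silent for a change that the Protocol itself classes as unacceptable toxicity.

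What is at stake is how the safety results read. A listing labelled as alerts could be empty for QTcF while some subjects exceed the 5.4.4 limits. No SAP text says that subjects above 500 ms, or more than 60 ms over baseline, will be counted as such.

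**Working it through.** **Inputs.** Alert rule, Table 6 limit (460 ms) and baseline definition: SAP 8.5. Limits of 500 ms and 60 ms: Protocol 5.4.4. Screening cap of 450 ms: Protocol 3.2. The documents state no derived figure on this point, so there is none to reproduce.

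**Step 1: the smallest rise that can be a high-QTcF alert.** With baseline B and on-study value x, the rule needs x > 460 and (x − B)/B > 0.25, that is x > max(460, 1.25 B). The rise must therefore exceed max(460 − B, 0.25 B). The first term falls with B and the second grows, so the minimum is where they meet: 460 − B = 0.25 B, giving B = 460/1.25 = 368 and a rise of 460 − 368 = **92 ms**.

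| Baseline (ms) | Alert needs a value above (ms) | Alert needs a rise above (ms) |
|---|---|---|
| 368 | 460 | 92 |
| 380 | 475 | 95 |
| 400 | 500 | 100 |
| 420 | 525 | 105 |
| 450 | 562.5 | 112.5 |

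Every rise above 60 and up to 92 ms thus meets the 5.4.4 change limit and cannot be a high-QTcF alert. The one formal exception is a value that rises but stays under the low limit of 295 ms. That needs a baseline below 295/1.25 = 236 ms.

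**Step 2: a reading just above 500 ms.** At x = 501 the alert needs B < 501/1.25 = 400.8. With a baseline of about 401 ms or more, 501 ms is not an alert. At 520 ms the corresponding baseline is 416, and at 550 ms it is 440.

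**Step 3: what the notable listing catches.** Since 500 > 460, every reading above 500 ms is listed there, whatever the change.

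**Step 4: what neither listing catches.** A rise of more than 60 ms that ends at or below 460 ms needs B + 60 < 460, so B < 400. Example: 390 to 455 is +65 ms, or 65/390 = 16.7%. It is not above 460, so it is neither notable nor an alert.

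Protocol Table 10 sets the QTcF limit at 450 ms, not 460. With 450 the smallest alert rise is 90 ms (B = 360). This example would then be listed as notable, and the gap would begin below a baseline of 390 (for example 380 to 445, +65 ms).

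**Step 5: can the number of subjects missing the alert label be stated?** Only with an assumed baseline distribution. Taking a normal distribution truncated at 450 ms, with mean 380 to 430 and SD 15 to 25, the share missing the label runs from 8% to 97% at a reading of 501 ms and from 1% to 81% at 520 ms. The assumption decides the answer.

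**The case against.** The strongest reply is that nothing is hidden. The notable listing has no change condition and prints the values, so a reader sees a 510. Change from baseline is summarised at each scheduled visit. Appendix A plans the QT/QTcF outlier table and also Table 3.5.7 on clinically significant ECG abnormalities. The alert is an extra that Protocol 9.4.2.4 never promised, patterned on the Protocol's vital-sign rule, and nothing requires it to mirror 5.4.4.

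Most of this stands, and it rules out three stronger readings that someone might take from the 92 ms figure.

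- *That most subjects above 500 ms go unflagged.* All of them are in the notable listing. The share without the alert label is unknown (Step 5).
- *That the report would contradict the treatment discontinuations.* The alert listing neither triggers nor records them. A test result that requires a change in study drug is an adverse event under Protocol 8.1.1, so a QT-driven stop would appear in the SAP's summaries of adverse events leading to discontinuation and in disposition (SAP 8.2.4 and 6.2).
- *That subjects are less well protected.* Protocol 7.5.4 says: "The 12-lead ECGs will be interpreted by the investigator at the site to be used for immediate subject management". The SAP listing plays no part in that.

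The reply does not close Step 4. Visit-level summaries describe the cohort and do not identify the subject who went from 390 to 455. Table 3.5.6 could do so, but its limits are not stated.

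**Conclusion.** The point holds as a minor weakness in safety reporting. As written, the alert cannot fire for a QTcF rise above 60 and up to 92 ms, nor for 501 ms from a baseline of about 401 ms or more. A rise of more than 60 ms from a baseline below 400 ms that ends at or below 460 ms is in neither ECG listing. No SAP text sets the > 500 ms or > 60 ms categories.

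These results are exact and need no distributional assumption. They rest on the Table 6 limit of 460 ms and on reading the percentage change as relative to the SAP's averaged baseline. That average can include pre-dose readings other than the screening one, so 450 ms is not a strict ceiling on it. The number of subjects affected cannot be given. No efficacy endpoint and no rule for managing subjects is touched.

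**What to change.** In SAP 8.5, replace the 25% condition for QTcF with the two limits already in Protocol 5.4.4, used as reporting categories: on-study value > 500 ms, or increase > 60 ms over baseline. State the same categories as the limits for Table 3.5.6. Protocol 5.4.4 and Table 3.5.6 also name uncorrected QT, so say whether the categories apply to it too. Keep the percentage rule for PR (25%) and QRS (30%). Section 5.4.4 is not changed.

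If the sponsor prefers to keep the alert rule as it is, stating the Table 3.5.6 categories alone would close most of the gap.

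In the same edit, reconcile the QTcF notable limit (450 ms in Protocol Table 10, 460 ms in SAP Table 6) with SAP 10.1, which reports no changes to Protocol-defined analyses.

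The cost is one or two sentences and minor programming on data already collected. The downside is a few more listed values.
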